- DSMB report will be submitted to NIH within one week after each quarterly scheduled meeting. However, any action by the DSMB resulting in a temporary or permanent suspension of the clinical study will be reported to the NIH Program Official responsible for the grant within 48 hours. Any death will requires expedited reporting to NIH program officer within 24 hours of study's knowledge of death.

Reportable Adverse Events, including Serious Events

Definitions

Adverse Event (AE), also referred to as an adverse experience, is any untoward medical occurrence in humans, whether or not considered intervention related, which occurs during the conduct of a clinical trial. Any change in clinical status, routine labs, x-rays, physical examinations, etc., that is considered clinically significant by the study investigator is considered an AE. Adverse events will include: hypothermia (defined as temp less than 35.5 degree C), abnormal changes in vital signs including respiratory rate (apnic episodes or respiratory rate more than 70/min), heart rate (less than 70/min or more than 220/min), and oxygen saturation (less than 85%), . The staff nurses normally records any abnormal vital signs findings as part of their routine NICU care for all babies. These data will continuously be recorded during the cold feeding (usually around 15 minutes). Changes in vital signs can be a routine and frequent occurrences in preterm babies as part of their pathophysiology, The following AEs if occurred during the cold feeding will result in study termination for that baby and notification of the DSMB committee:

- 1- Any incidence of hypothermia
- 2- More than 2 episodes of apnea
- 3- Tachypnea defined as increase respiratory rate more than 70/min for more than 2 minutes
- 4- More than 2 episodes of bradycardia (defined as HR less than 70 for more than 10 seconds).
- 5- Tachycardia (defined as HR more than 220) for more than one minute

6- More than 2 episodes of desaturation (defined as O2 saturation less than 85%) for more than 30 seconds

Serious Adverse Events (SAEs), as determined by the PI, are any event that results in any of the following outcomes:

- 1. Death
- 2. Life-threatening SAE (life-threatening means that the study participant was, in the opinion of the investigator, at immediate risk of death from the reaction as it occurred)
- 3. Inpatient hospitalization or prolongation of existing hospitalization
- 4. Persistent or significant incapacity or substantial disruption of the ability to conduct normal life function.
- 5. Important medical event that may not result in one of the above outcomes, but may jeopardize the health of the study participant or require medical or surgical intervention to prevent one of the outcomes listed in the above definition of SAE.

Participants in these studies will likely have pre-existing medical conditions, those pre-existing conditions will not be reported as adverse events. New events or the worsening through frequency or intensity of pre-existing conditions will be reported as adverse events within the context of the study.

Elicitation of Adverse Events and Serious Adverse Events

AEs and SAEs may be discovered through any of these methods:

- Observing the participant by the research team
- Observing the participant by the NICU team caring for the baby (which will be done in an objective manner)
- Questioning the participant's parent or legal guardian (which will be done in an objective manner)
- Receiving an unsolicited complaint from the NICU medical team and/or participant's parent or legal guardian
- Reviewing of medical records/source documents

The PI and study staff will review all data collection forms on an ongoing basis for data completeness and accuracy as well as protocol compliance. It is anticipated that data verification will be performed by someone other than the individual originally collecting the data, or by double-data entry. A statement reflecting the results of the ongoing data review will be incorporated into the Annual Report for the Independent Monitor

Reportable AEs and SAEs will be documented on the Adverse Event Form first and will be recorded within the participant's records. Source documents, including copies of electronic medical records may be attached to the record when requested. Only the participant's study ID will be provided on source documentation, all other protected health information (PHI) must be redacted prior to report submission.

Assessment of Severity:

The PI will review all adverse events for seriousness (AE or SAE), severity (e.g. Grade 1-3) and causality during review of medical records, and will consult with other research personnel as needed. The investigator will document (signature/date) an assignment of severity (e.g., Grade 1-3) and make the initial determination of the causality of the event to the study intervention/procedures. The investigator may not delegate someone other than a clinician licensed to make diagnoses to this responsibility. The results will be submitted to the DSMB for review, verification and taking appropriate action as needed.

Guidelines for Assessing Severity of an Adverse Event

- The PI/DSMBwill use the following definitions when assessing severity of an Adverse Event:
 - Grade-1/ MILD: Participant has minor findings, but tolerates them well and no or minimal intervention is required
 - Grade-2 / MODERATE: Participant experiences enough symptoms or findings to require intervention
 - Grade-3 / SEVERE: Participant experiences symptoms or findings that require significant intervention

Guidelines for Determining Causality of an Adverse Event

The PI/DSMB will use the following question when assessing causality of an adverse event to the study product/intervention: Is there a reasonable possibility that the study product/intervention caused the event? "Reasonable possibility" means that there is evidence to suggest a causal relationship between the study intervention/procedures and the adverse event. An affirmative answer designates the event as a suspected adverse reaction.

SAE Reporting and Management Procedures

- Study staff will be trained to extract, evaluate, and report adverse events according to the protocol requirements
 and under the direct supervision of the PI. Unexpected, serious, and intervention-related serious adverse events
 (SAEs) will be reported to the DSMB, NYU IRB, and NIH immediately. Any adverse events, breaks of
 confidentiality, or any other data or safety issues that arise will be immediately brought to the attention of the
 NYU- IRB. All events will be reported within 24 hours of having received notice of the event. [name] and Dr.
 [name] will be responsible for completing an Adverse Events Form should an event occur.
- The following information will be reported for each event and must be reviewed by the investigator or designee: 1) description of the event, 2) start date, 3) stop date, 4) severity of the event, 5) causal relationship to study product/intervention, 6) seriousness, 7) outcome of the event, and 8) if action with study product/intervention was required.
- Drs. [name], [name] and [name] will collaboratively gather any information needed to investigate the event and to determine subsequent action. Any subsequent action will be documented and reported to the NYU IRB and the Program Officer at NICHD. Adverse event reports will be reported in the annual continuing review report to the NYU IRB to ensure participant safety. Procedures to protect patient confidentiality and systems to ensure secure file transfer of sensitive data will be in place.

Study Halting/Termination:

The study will stop immediately if any of the following is to occur:

- 1- Any Serious Adverse Events (SAEs), as detailed in the Data and Safety Monitoring Plan, will result in the immediate stopping of the study. The SAE will be reported immediately (within 48 hours) to the Data Safety Monitoring Board (DSMB) and the NIH program officer responsible for the study. Any death will requires expedited reporting (within 24 hours of study's knowledge of death). No further enrollment will be allowed until the DSMB determines that this event was unrelated to the study procedures.
- 2- Frequent AEs as a result of cold milk feeding that deemed to be excessive by the PI or the DSMB will trigger study halting. No further enrollment will be allowed until the DSMB determines that these events were unrelated to the study procedures.
- 3- The decision by the DSMB to halt the study at any time point at their discretion. Any action resulting in a temporary or permanent suspension of the clinical study will be reported to the NIH Program Official responsible for the grant. During the funding of this study, any action by the FDA (if applicable), NYU IRB or one of the study investigators that results in a temporary or permanent suspension of the study will be reported to the NIH Program Official immediately.

Research Use of Stored Human Samples, Specimens, or Data

Intended Use:

Data collected under this protocol may be used to study efficacy and safety of cold liquid feedings. Human samples and/or specimens will not be obtained.

Storage:

Data will be stored using codes assigned by the investigators. Data will be kept in REDCap.. Only investigators will have access to the data.

Data Handling and Record Keeping

Once the data is collected on the data collection sheet, they will be immediately assigned a unique identifier. No link between this identifier and patient information will be made. No protected information or patient identifiers will be collected either. The data collected will be entered into RedCap within 2 days of collection. The original copies of the consent will be kept in a locked file cabinet. Consent forms will be kept in a secure location for up to six years in accordance with institutional policies.

Future Use of Stored Specimens

There will be no collected biospecimens to be stored.

Study Finances

Funding Source NIH R21 Grant

Costs to the Participant

None

Participant Reimbursements or Payments

None

DISSEMINATION PLAN FOR CLINICAL TRIAL:

This clinical trial does not meet the criteria for an "applicable clinical trial" since this study does not involve the use of any drug, biological or device products. The Principal investigator (PI) will assume the role of the responsible party and will ensure compliance to the NIH policy on dissemination of NIH-funded clinical trial information.

Registering at ClinicalTrials.gov:

This trial will be submitted for approval to the NYU- Langone Long Island Hospital University Hospital Institutional Review Board and no patient enrollment will occur without IRB prior approval. In accordance with the NIH policy on dissemination of NIH-funded research, this clinical trial will be registered at ClinicalTrials.gov not more than 21 days of enrollment of the first study participant.

Submitting results to ClinicalTrials.gov:

The PI will be the responsible party to report the clinical trial information. Registration information including descriptive information, recruitment information, location and contact information of the study PI and administrative data will be submitted.

The date of the last participant receiving an intervention will be reported as the primary completion date. In the event that the study enrollment is terminated prematurely, the study findings as well as reasons for early termination of the study will be made available on clinicaltrials.gov. All the results are submitted to clinicaltrials.gov within 12 months of primary completion date.

	Action	Timeline
1.	Register on ClinicalTrials.gov	Within 21 days of first patient enrollment
2.	Results information entered on ClinicalTrials.gov	Within 12 months of primary completion date

Making results publicly discoverable:

The results of the study will be submitted to ClinicalTrials.gov for public posting, including inconclusive results that do not amount to a publication, thus ensuring that the research findings are publicly available. The results information reported will include participant baseline characteristics, outcomes and statistical analyses, the protocol and statistical analysis plan, and administrative information. Adverse events pertaining to the study interventions and protocol deviations will also be submitted to ClinicalTrials.gov. In addition, all manuscripts published will be made publicly available on Pubmed Central.

Informed consent:

We will include a specific statement in the informed consent documents about posting of the clinical trial information at Clinical Trials.gov. This information will be discussed with the study participants prior to obtaining consent for study enrollment.

Monitor and manage data quality:

We will conduct internal quality checks, such as automatic range checks, to identify data that appear inconsistent, incomplete, or inaccurate. The study staff will participate in a start-up meeting during which time the protocol will be reviewed and discussed and formal training will occur with regard to the assessments, rating scales being used, procedures for data entry and management.

7. Bibliography:

- 2. National Vital Statistics Reports Vol. 66, No. 1. January 5 2017.
- 5. Lemons PK. From gavage to oral feedings: just a matter of time. *Neonatal network : NN.* Apr 2001;20(3):7-14.

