Endpoint	The primary outcome will be the percentage of swallows with aspiration and/or penetration for cold milk compared with room temp milk (a total of 15 swallows will be assessed by VFSS and FEES). Based on our preliminary results, we expect to find a significant decrease in penetration and aspiration during the initial cold swallows (5 swallows). We expect this improvement to be sustained on the subsequent cold swallows (10 swallows) following the 15-minute cold liquid feeding. A decrease of 30% in penetration and/or aspiration with cold milk will be considered significant. Similarly, a 30% improvement of feeding coordination as assessed by nFant device will be considered significant.
	2. Evaluate the safety of feeding cold milk in preterm infants. We will evaluate whether cold milk will cause hypothermia (assessed by measuring Axillary temperatures), change in vital signs (respiratory rate, heart rate, and oxygen saturation) as well as change in mesenteric blood flow indices (assessed by abdominal ultrasound) These changes with cold milk feeding will be expressed as % change compared to base line (room temp milk).
Study Duration	2 years
Participant Duration	The subjects will participate in the study for approximately 48 hours during their NICU hospital stay
Population	Preterm Infants less than 34 weeks gestation admitted to NYU- Langone Long Island Hospital NICU. (n=42)
Study Sites	NYU- Langone Long Island Hospital
Number of participants	42

1. Introduction, Background Information and Scientific Rationale

Approximately half a million preterm infants are born every year in the USA.^{1,2} It is estimated that 30-70% of very low birth weight (VLBW) preterm infants will be diagnosed with swallowing dysfunction (dysphagia), with an inverse relationship between the severity of dysphagia and gestational age (GA).³⁻⁶ Although the pathophysiology of dysphagia is multifactorial,^{4,7-9} the discoordination between swallowing and breathing is the most prevalent cause of dysphagia in preterm infants,¹⁰ which often leads to airway compromise in the form of laryngeal penetration and/or tracheal aspiration into the lungs.^{7,11} Chronic airway compromise results in a persistent inflammatory state, with disease progression to chronic lung injury and *bronchopulmonary dysplasia (BPD)* that can be devastating for already fragile and developmentally immature lungs in preterm infants.^{4,7}

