- The axillary temperature will be measured immediately prior to and after each feeding condition. It will also be measured at 10, and 30 minutes after the CS feed, at the same time the gastric content temperatures are taken. Infants' vital signs will be recorded (blood pressure, respiratory rate, heart rate, and oxygen saturation), as well as evidence of bronchospasm, lethargy, respiratory distress, apnea, tachypnea, cyanosis, bradycardia, or tachycardia.
- Doppler ultrasound (Sonosite Edge Ultrasound system, Sonosite, Inc, WA) will be used to measure
 intestinal blood flow indices including the superior mesenteric artery flow (SMA), peak systolic velocity,
 SMA mean velocity, SMA end-diastolic velocity, resistive index, pulsatility index, portal vein volumetric
 blood flow, as well as heart rate and mean arterial blood pressure. Intestinal blood flow monitoring via
 Doppler ultrasound will be performed 6 times for each participant, performed one hour before and at 30 and
 60 minutes after both bedside feeding conditions (RTS and CS). Measurements will be taken at the bedside
 in the supine position.
- Step 2 (done 24-48 hours after step 1):
 - Infants will be transported to the radiology suite and undergo VFSS and or FEES, as ordered by the treating
 medical team (Figure1: the blue boxes indicate procedures done for research purpose only. None of the
 research procedures are experimental and are approved tests for neonates including VFSS, FEES, nfant
 test and abdominal ultrasound).
 - Routine procedure for VFSS or FEES will be followed as ordered by the medical team. This procedure is part of the routine clinical care and not considered part of the research study.
 - If no dysfunction is noted, the procedure will end, and the child will no longer be eligible for further participation in this research study. If dysfunction (penetration/aspiration) either on the VFSS or FEES study is noted, the child will be eligible to participate in the next phase of the study.
 - Immediately following the initial VFSS-FEES assessment, the infants will remain in the same seated position with the FEES scope in place. While keeping all variables from the standard VFSS-FEES the same, the infant will be fed cold barium (4-9°C) using the same nipple. A total of 5 swallows will be visualized using VFSS and FEES, labeled "Cold Swallows-1 (CS1)." These 5 swallows assessment are done for the research purpose only.

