 - If the dysphagia didn't improve, the study would end, and the child will no longer be eligible for participation further in this research study.
 - If the dysphagia improves with cold liquid, VFSS will then be turned off and the infants will then be fed their regular feeds (formula or expressed breast milk as indicated by the medical team) chilled to an approximate temperature of 4-9°C for a total of 15 minutes, or until the infant shows signs of feeding completion. The cold feeding will be replaced every 5 minutes to make sure that the temperature is maintained at 4-9°C to minimize habituation effect.³⁰
 - After the 15 minute period, the infant will be re-assessed by VFSS-FEES using cold barium from the same bottle (10 swallows, labeled "Cold Swallows-2" [CS2]). This design evaluates whether a full feeding of cold liquid will result in decreased penetration or aspiration compared to RTS condition. These 10 swallows assessment are done for the research purpose only).
 - The axillary temperature will be monitored every 10 minutes. Infants' vital signs (blood pressure, respiratory rate, heart rate, and oxygen saturation), as well as evidence of any respiratory compromise, will be recorded. A neonatologist will be next to the baby at all times. The baby will return to the NICU after the study accompanied by the NICU team, including the neonatologist.

Study #: i20-00876

Version Date: 6/13/2022

Depending on the scheduling of the VFSS/FEES testing by the infant's medical team, the research team might need to do Step 2 before Step 1, as described above. There will be at least 24 hours period between the two steps.

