Statistical Analysis and Estimated Sample Size: To evaluate whether cold liquid will improve aspiration and penetration, event rates during CS compared to RTS, as well as corresponding 95% confidence intervals, will be computed. Aspiration and Penetration variables will be assessed for normality using histograms and the Kolmogorov-Smirnov (K-S) test. Wilcoxon Signed-Rank test will be used to evaluate the specific aim 1, i.e., compare changes in aspiration and penetration between RTS and CS. Aspiration and penetration will be evaluated using different methods (FEES and VFSS). Power and Sample Size: Our preliminary data showed a mean change of 44 and 36% in aspiration and penetration, respectively. For power computation, we conservatively assumed an average change of 30% and a common standard deviation of 25 in both aspiration and penetration. We simulated data using a two-sided Wilcoxon Signed-Rank Test (the non-parametric equivalent of the paired t-test) with alpha=0.05 significance level and a pre-post correlation of 0.20, which revealed that a sample size of N=25 subjects would provide us more than 95% power to detect a large effect size both in aspiration and penetration. These simulation results are based on 10000 Monte Carlo samples. Assuming a conservative estimate that 60% of infants with clinical dysphagia will have a positive VFSS or FEES test, we expect that we will need to enroll 42 subjects to have 30 subjects with a positive dysphagia test. NYU- Langone Long Island Hospital Hospital NICU is a Regional Perinatal Center (one of 17 NICUs in the state of New York designated to provide the highest level of care to neonates in NY State). The average number of VLBW infants admitted is 90-100/year and at least 40-45 infants/year will have clinical dysphagia referred for VFSS-FEES testing (3-4 patients/month). Therefore, we are confident that we will have sufficient sample size over the 2-year grant period to conduct the proposed aims.

2: Evaluate the safety of feeding cold milk in preterm infants.

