Our preliminary data (REF) showed a mean change of 44 and 36% in aspiration and penetration, respectively. For power computation, we conservatively assumed an average change of 30% and a common standard deviation of 25 in both aspiration and penetration. We simulated data using a two-sided Wilcoxon Signed-Rank Test (the non-parametric equivalent of the paired t-test) with alpha=0.05 significance level and a pre-post correlation of 0.20, which revealed that a sample size of N=25 subjects would provide us more than 95% power to detect a large effect size both in aspiration and penetration. These simulation results are based on 10000 Monte Carlo samples. Assuming a conservative estimate that 60% of infants with clinical dysphagia will have a positive VFSS or FEES test, we expect that we will need to enroll 42 subjects to have 30 subjects with a positive dysphagia test.

Informed Consent Process

Informed consent is a process that is initiated prior to the individual's agreeing to participate in the study and continues throughout the individual's study participation. Extensive discussion of risks and possible benefits of participation will be provided to the infants' parents. Consent forms will be IRB-approved and the parents (defined as either the mom or dad if they are legally married) will be asked to read and review the document. The study investigators will explain the research study to the parents and answer any questions that may arise. All participants will receive a verbal explanation in terms suited to their comprehension of the purposes, procedures, and potential risks of the study and of their rights as research participants. Parents will have the opportunity to carefully review the written consent form and ask questions prior to signing. The parents should have the opportunity to discuss the study with their surrogates or think about it prior to agreeing to participate. The parents will sign the informed consent document prior to any procedures being done specifically for the study. The parents may withdraw consent at any time throughout the course of the study. A copy of the signed informed consent document will be given to the parents for their records. The rights and welfare of the participants will be protected by emphasizing to them that the quality of their medical care will not be adversely affected if they decline to participate in this study.

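### The stated primary outcome, a composite of aspiration and/or penetration, is neither tested nor powered; its components are, with no rule for which decides, and the full-feed comparison exists only in infants selected for improving

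*Combined protocol and SAP*

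**What the plan says.** **Outcome.** The Endpoint row of the Synopsis gives a single composite: "The primary outcome will be the percentage of swallows with aspiration and/or penetration for cold milk compared with room temp milk". It attaches a swallow count, "a total of 15 swallows will be assessed by VFSS and FEES", split into five initial cold swallows and ten after a 15-minute cold feed. It then adds "A decrease of 30% in penetration and/or aspiration with cold milk will be considered significant".

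**Analysis.** The Statistical Considerations check aspiration and penetration as separate variables for normality, then state: "Wilcoxon Signed-Rank test will be used to evaluate the specific aim 1, i.e., compare changes in aspiration and penetration between RTS and CS".

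**Power.** The Statistical Considerations, repeated in Section 6, cite preliminary changes of 44 and 36% for aspiration and penetration respectively. They assume a change of 30% with a common SD of 25 for both, and conclude that "a sample size of N=25 subjects would provide us more than 95% power to detect a large effect size both in aspiration and penetration".

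**Who contributes which swallows.** Under Section 4, Step 2, the room-temperature study (RTS) comes first: "If dysfunction (penetration/aspiration) either on the VFSS or FEES study is noted, the child will be eligible". For the cold swallows labelled CS1, "A total of 5 swallows will be visualized using VFSS and FEES". If the dysphagia does not improve at CS1, "the study would end, and the child will no longer be eligible for participation further in this research study". Only improvers receive the 15-minute cold feed and the ten CS2 swallows. The analysis text refers to the cold condition only as CS.

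**The concern.** Followed literally, the plan produces two test results on two components and none on the outcome it calls primary. No passage says whether the composite, one component or both must succeed, and none mentions multiplicity. The same data could then be reported as positive or negative depending on a choice made after they are seen. The Safety Monitoring Plan has interim results presented to the monitoring board after every ten patients, which is a further reason to fix the deciding variable in advance.

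The swallow set raises a second problem. A 15-swallow percentage exists only for infants who improved at CS1. If the primary or full-feed comparison is made in those infants, they have been selected on their own outcome, and regression to the mean will look like a benefit of cold milk. Section 4 says that if efficacy and safety are demonstrated, clinicians can use cold milk without repeating the study's measures in each child, so the estimate has to mean what it appears to mean.

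**Working it through.** **1. The plan's own power figure.** Inputs from the Statistical Considerations: N = 25, mean fall 30, SD 25, pre-post correlation 0.20, two-sided 0.05.
- SD of the paired difference = 25 × √(2 × (1 − 0.20)) = 31.6.
- Standardized effect = 30 / 31.6 = 0.95.
- Simulated Wilcoxon signed-rank power, with normal differences: 99%.

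The claim of more than 95% is reproduced for each component.

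**2. Power for the composite.** The documents give no effect or SD for it. The same calculation with assumed inputs at N = 25 gives:

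| SD | Fall 30 | Fall 36 |
|---|---|---|
| 25 | 99% | >99% |
| 30 | 96% | 99% |
| 35 | 89% | 97% |
| 40 | 79% | 91% |

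Power falls below 95% only if the SD is assumed well above the stated 25. This does not show that the composite is underpowered. It shows that the plan's figure cannot be carried over without stating the composite's inputs.

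**3. Cost of an open decision rule.**
- Two tests at 0.05, either sufficient, independent: 1 − 0.95² = 9.75%.
- Simulated at N = 25: 9.5% at a between-component correlation of 0, falling to 7.4% at 0.8. The correlation is assumed.
- If both components must succeed at 0.05, power is about 98.8%. With each tested at 0.025, it is 98.2% per component.

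Any of these rules is affordable with the stated inputs. What is missing is the choice.

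**4. Selection at CS1, with no true effect.** The assumptions are:
- each infant has a stable event rate, the same warm and cold, drawn from a beta distribution with mean 30 to 70% and SD 15 to 25 points;
- there are 5, 10 or 15 RTS swallows, and the infant is kept if at least one shows an event;
- CS1 has 5 swallows and CS2 has 10;
- improved means that the CS1 percentage is below the RTS percentage.

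Average RTS minus cold, in percentage points:

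| Comparison | Spurious shift favouring cold |
|---|---|
| CS2, improvers only | 4.5 to 16 |
| All 15 cold swallows, improvers only | 9.5 to 21 |
| CS1, all test-positive infants | 0 to 6 (at most 1.5 with 10 or 15 RTS swallows) |

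The improver requirement selects infants whose RTS result was high by chance, so even a fresh CS2 sample looks better. The 15-swallow percentage also contains the CS1 swallows on which selection was made, so its shift is larger. The largest values arise with 5 RTS swallows and the smallest with 15.

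**The case against.** The strongest case on the other side is that power is ample. The assumed change of 30 is below the preliminary 44 and 36, the stated power reproduces, and joint or Bonferroni rules cost almost nothing. That stands: a reader might infer that the trial is underpowered for its primary outcome, but the documents give no composite effect or SD from which to show it.

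A reader might also infer that the 30% statement contradicts the 0.05 test. Read as a threshold on the observed absolute group mean, it would: at a true fall of 20 points with SD 25, the test is significant in 84% of samples, and 78% of all samples are significant with a mean below 30. No passage adopts that reading. The same 30 is the assumed average change in the power text, and the phrase may mean clinical importance. What stands is that the scale (absolute or relative) and the level (infant or group) are not stated.

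A third tempting reading is that scoring by VFSS and FEES biases the comparison. Section 4 keeps all other conditions of the standard examination the same for the cold swallows, and the analysis text says that both methods will be used. No primary method is named, but that is missing detail rather than a demonstrated bias.

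Finally, the documents do not say that the analysis is restricted to improvers, and the Synopsis already separates the initial swallows from the sustained ones. This is fair, but CS2 does not exist for anyone else, so any full-feed comparison is restricted by design. The aim of preliminary evidence softens the consequence without settling which result decides.

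**Conclusion.** The plan should be changed on two counts. First, the stated primary outcome has no test and no power statement, while its two components have both, uncorrected and without a decision rule. That much follows from the text alone. If either component may succeed, the false-positive rate is about 7 to 10%; the range rests on an assumed between-component correlation of 0 to 0.8, with 9.75% for independence.

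Second, full-feed and 15-swallow results exist only in infants selected for improving at CS1. The direction of this bias follows from the design. Its size, about 4.5 to 16 points for CS2 and 9.5 to 21 for all 15 swallows, depends on the assumed infant rates, RTS swallow counts and definition of improvement. Against a planned effect of 30 it is not negligible.

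The power calculation for the components is correct as stated. Neither a shortfall in composite power nor a contradiction between the 30% statement and the test is established.

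**What to change.** 1. Name one primary test: a two-sided 0.05 Wilcoxon signed-rank test on the per-infant composite percentage, RTS versus cold. Make aspiration and penetration secondary.
2. State which cold swallows form the primary percentage, and include every test-positive infant who has CS1. Report CS2 and 15-swallow results as conditional on improvement at CS1, not as an unselected estimate of the full-feed effect. Whether CS1 is the primary set is the sponsor's choice: it is the only set planned for every test-positive infant, but the study question is the full feed and a five-swallow effect has already been reported (Section 1). A percentage over whatever cold swallows an infant has would rest on 5 for non-improvers and 15 for improvers, so the rule needs to be explicit.
3. Attach the power statement to the composite, with its assumed effect and SD.
4. Reword the 30% statement as a clinical-relevance benchmark with its scale and level given, so that it does not compete with the 0.05 test.

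The cost is wording in the Synopsis and the statistical sections plus one rerun of the simulation; no study procedure changes. The downsides are that component results become secondary, the restated power may differ from the present figure, and the full-feed conclusion is limited to infants who improved at CS1. If CS1 is chosen, selection on a positive RTS study still leaves a shift of 0 to 6 points favouring cold under the assumptions above, and this should be acknowledged in the report.
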